#### 7.6.2 Secondary Efficacy Analysis

##### 7.6.2.1 Clinical Improvement Score as Measured by WHO COVID-19 Clinical Improvement Ordinal Scale

Clinical improvement measured as a score on the WHO COVID-19 Clinical Improvement Ordinal Scale will be analyzed using an ordinal logistic regression on Days 7, 14, and 28, with study treatment, clinical improvement score at baseline (as numerical variable), age at baseline ( $> 65$  years vs  $\leq 65$  years), and remdesivir or other authorized treatments for COVID-19 use at baseline (yes vs no) as covariates. The p-value for treatment effect will be provided based on the Wald test.

In addition, descriptive statistics will be provided for average score by treatment group, and the proportion of patients at or below each score, at each visit.

Time to 2-point improvement from baseline in WHO COVID-19 Clinical Improvement score, time to score of 2 or lower, and time to score of 0, will also be analyzed. The hazard ratio and its 95% confidence interval for these time-to-event endpoints will be estimated by Cox proportional hazard model, with treatment, remdesivir or other authorized treatments for COVID-19 use at baseline (yes vs no) and age at baseline ( $> 65$  years vs  $\leq 65$  years) as covariates. The analysis will be carried out using two different censoring rules: 1) Patients will be censored at the time they are provided any authorized treatment for COVID-19 not prescribed at baseline, or on Day 28 if they have not yet recovered or have died by Day 28; 2) Patients will only be censored on Day 28 if they have not yet recovered or have died by Day 28. The p-value for comparison between treatment groups will be obtained based on the Cox proportional hazards model described above. Median time to 2-point improvement, time to score of 2 or lower, and time to score of 0 will be estimated by Kaplan-Meier (KM) method, and the KM curve will be provided.

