4.1. Inclusion Criteria

Patients must satisfy all of the following criteria at the screening visit unless otherwise stated:

1. Willing and able to provide informed consent.
2. Male or female patients between 18 and 80 years of age.
3. Oxygen saturation <94% in room air at screening.
4. Hospitalized with mild COVID-19 disease (not requiring oxygen therapy [WHO COVID-19 Clinical Improvement Ordinal Scale, score of 3] or requiring oxygen therapy by mask or nasal prong [WHO COVID-19 Clinical Improvement Ordinal Scale, score of 4]). Requirement of oxygen therapy by mask with reservoir to treat severe COVID-19 pneumonia is not allowed for enrollment.
Note: Hospitalized patients can also include patients admitted to centers conditioned as hospitals to treat COVID-19 patients.
5. Chest x-ray or CT scan consistent with pneumonia.
6. Onset of COVID-19 symptoms within 2 weeks prior to randomization.
7. SARS-CoV-2 infection confirmed by a PCR test, antigen, or any authorized commercial or public health assay (nasopharyngeal, oropharyngeal, or respiratory samples, not serology testing).
8. Male patients and female patients of childbearing potential must agree to use protocol-specified methods of contraception ([Appendix 4](#)).
9. Female patients of childbearing potential must have a negative pregnancy test at screening or pretreatment on Day 1.
10. Male patients must agree not to donate sperm from the first dose through 90 days after the last dose of study treatment; female patients of childbearing potential should refrain from donation of ova from Day 1 until 90 days after the last dose of study treatment.
11. Patient is, in the opinion of the investigator, willing and able to comply with the study treatment regimen and all other study requirements.

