### 2.3 Sample Size

A total of 174 patients are planned to be randomized into the study:

- 20 patients in the sentinel cohort (10 patients in each treatment group)
- 154 patients in the expansion cohort (77 patients in each treatment group).

This enrollment level ensures 80% power to demonstrate proof of concept efficacy with one-sided alpha of 0.2.

The sample size is based on the following assumptions:

- The randomized allocation ratio is 1:1 between the antroquinonol group and the placebo group
- The proportion of patients alive and free of respiratory failure is approximately 78% on placebo vs 89% on antroquinonol

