## Statistical Analysis Plan

Sponsor Name: Golden Biotechnology Corporation

Sponsor Protocol ID: GH Covid-2-001

Covance Study ID: 000000203201

Visit	Target Day of Visit a	Acceptable visit window
Day 3	Day 3	Days 2 to 3
Day 5	Day 5	Days 4 to 6
Day 7	Day 7	Days 7 to 8
Day 14 - EOT	Day 14	Days 14 to 16
Day 28 - Follow up	Day 28	Days 26 to 30

a relative to the date of first dose of study treatment.

For all populations, multiple visits within the same window will be dealt with as follows:

- If both scheduled and unscheduled visits fall within the same visit window, the scheduled visit will be used for analysis.
- If multiple scheduled visits occur within a single visit window, then the visit closest to the target day of the visit window will be used in the analysis. If there is a tie, the later visit will be used in the analysis.
- If multiple unscheduled visits occur within a single visit window (with no scheduled visit within the window) then the unscheduled visit closest to the target day of the visit window will be used in the analysis. If there is a tie, the later unscheduled visit will be used in the analysis.

Baseline value is defined as the last scheduled or unscheduled value collected prior to the first dose of study treatment. Assessments carried out on day of first study treatment administration are considered to have taken place before the study treatment administration, if the corresponding times have not been recorded.

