## 6.2 Handling of Dropouts, Missing Data, and Outliers

Unless specified otherwise, no imputation for missing/partial dates will be performed for missing safety, efficacy, PK variables. For time-to-event efficacy variables, the censoring rules for no event data will be included in efficacy analysis section.

For patients with clinical improvement score above 2 or missing at discharge, missing scores on the next day after discharge will be imputed to 2. After above rule implemented, missing scores will be imputed using Last Observation Carried Forward for a maximum of 1 day at Day 7, 2 days at Day 14, and 4 days at Day 28.

Dates in original form will be used in all listings.

No rules for outlier detection are planned.

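### Time to 2-point WHO improvement has a different target for score-3 and score-4 entrants, but its Cox model leaves out the baseline score

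*SAP*

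**What the plan says.** Protocol 4.1 admits hospitalised patients "not requiring oxygen therapy [WHO COVID-19 Clinical Improvement Ordinal Scale, score of 3] or requiring oxygen therapy by mask or nasal prong" (score 4). Time to 2-point improvement from baseline is a secondary endpoint (Protocol 2.2, SAP 3.2). Time to score 2 or lower and time to score 0 are labelled supportive. On the scale in Protocol Appendix 7, score 1 is ambulatory without limitation and score 2 is ambulatory with limitation.

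SAP 7.6.2.1 has the hazard ratio "estimated by Cox proportional hazard model, with treatment, remdesivir or other authorized treatments for COVID-19 use at baseline (yes vs no") and age group as the only terms. The ordinal logistic model in the same section does include "clinical improvement score at baseline (as numerical variable"). Protocol 8.4.2 gives the Cox model the covariates of the primary model, so the SAP follows the protocol. Protocol 5.3 stratifies randomisation by authorised-treatment use and age, not by WHO score.

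Under the second censoring rule, "Patients will only be censored on Day 28 if they have not yet recovered or have died by Day 28". SAP 6.2 adds: "For patients with clinical improvement score above 2 or missing at discharge, missing scores on the next day after discharge will be imputed to 2". Neither section says whether an imputed 2 counts as an event in the Cox model.

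**The concern.** On this endpoint the baseline score is more than a prognostic factor, because it fixes what the patient must achieve. A score-3 entrant has to reach 1 and a score-4 entrant has to reach 2. If one arm has more score-4 patients by chance, the planned model credits or debits the drug for that mix. The direction depends on which group reaches its own target sooner, which is not known in advance. When the two groups differ in speed, leaving the score out also pulls the hazard ratio toward 1.

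The imputation rule can sharpen the difference. If an imputed 2 counts as an event, the same discharge completes the endpoint for a score-4 entrant and not for a score-3 entrant.

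The 0.2 level matters because SAP 7.1 calls a result at one-sided 0.2 a promising trend.

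**Working it through.** **The plan's own figure.** Neither document gives an event count, hazard ratio or power for this endpoint. The stated design figure is for the primary endpoint: 174 patients, 80% power at one-sided 0.2, final odds-ratio boundary 0.697. It reproduces. SE(log OR) = √[1/(87·0.78·0.22) + 1/(87·0.89·0.11)] = 0.429, and exp(−0.8416·0.429) = 0.697. Simulated power with both futility rules applied is 79.5%. None of this concerns the Cox model.

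**Inputs from the documents.** 87 per arm; entry scores 3 and 4; follow-up to Day 28; scheduled visits on Days 3, 5, 7, 14 and 28; failure rates of 22% and 11% from "The proportion of patients alive and free of respiratory failure is approximately 78% on placebo vs 89% on antroquinonol".

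**Assumptions, not in the documents.** 50, 70 or 90% at score 4; exponential discharge time with placebo median Day 8; score-3 discharge hazard 1 or 1.5 times that of score 4. A score-4 patient has the event at discharge. A score-3 patient has it at discharge or, if staying at score 2, at the first scheduled visit after a lag of median 7 or 14 days. Failures have no event and are censored at Day 28. Efron ties and a Wald test were used; age and authorised-treatment use were not simulated. A hazard ratio above 1 favours antroquinonol.

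**Step 1: how large an imbalance.** The SD of the between-arm difference in the score-4 share is √[2q(1−q)/87]. A gap of 9 patients is 9/87 = 10.3 points. Probabilities are exact binomial.

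| Share at score 4 (q) | SD (points) | Gap ≥9, either direction | Gap ≥9, given direction |
|---|---|---|---|
| 50% | 7.6 | 19.7% | 9.9% |
| 70% | 6.9 | 15.9% | 8.0% |
| 90% | 4.5 | 3.2% | 1.6% |

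**Step 2: what that imbalance does with no drug effect.** Nine more score-4 patients on antroquinonol (48 vs 39, 65 vs 56, 83 vs 74 of 87), 3,000 trials per setting. Entries are the percentage positive at one-sided 0.2 / 0.025 in the model without score; ranges pool the three shares.

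| Failures | Half or all score-3 patients stay at 2 | None stay at 2 |
|---|---|---|
| None | 25.0–56.2 / 3.7–14.5 | 12.3–20.5 / 1.0–2.2 |
| 22% in both arms, unrelated to score | 22.5–39.7 / 3.1–6.8 | 16.4–20.8 / 1.6–2.9 |
| 22% in both arms, failure OR 4 (score 4 vs 3) | 14.5–36.4 / 1.4–6.5 | 9.5–14.0 / 0.6–1.4 |

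Mean hazard ratio without score is 0.93 to 1.18. Stratified by score it is 0.99 to 1.01, with 18.6–22.2% / 1.8–3.1% positive.

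A separately written simulation (600 null trials per setting, 65 vs 56) agrees. At one-sided 0.2, without score versus stratified: all stay 7 days, 41% vs 19%; half stay 7 days, 31% vs 18%; all stay 14 days, 51% vs 18%; none stay and score 3 discharged 1.5 times faster, 12% vs 19%.

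**Step 3: average type I error.** Without fixing the imbalance (4 settings, 5,000 trials each), the model without score rejects in 19.5–20.8% at 0.2 and 1.8–2.5% at 0.025. With score it rejects in 19.3–20.9% and 2.0–3.0%.

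**Step 4: power.** Change from stratifying, in percentage points at 0.2 / 0.025 (2,000 trials per setting):

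| Score-3 patients staying at 2 | No failures, discharge HR 1.4 | 22%/11% failing, discharge HR 1.15, failure OR 1 to 6 |
|---|---|---|
| None | −0.6 to +1.1 / −1.1 to +2.1 | −1.7 to +0.8 / −2.0 to +2.1 |
| Half, 7 days | +0.9 to +4.3 / +1.5 to +5.2 | −3.2 to +1.0 / −4.9 to +1.1 |
| All, 7 days | +3.1 to +10.3 / +5.3 to +13.6 | −2.8 to +2.4 / −5.2 to +3.1 |
| All, 14 days | +6.2 to +16.6 / +10.2 to +18.1 | +0.4 to +6.8 / +0.5 to +7.4 |

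If an imputed 2 is not an event, the change is −1.0 to +14.4 / −1.3 to +14.6 with no failures, and −2.4 to +4.5 / −3.6 to +5.5 with 22%/11% failing.

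**Step 5: attenuation in a simpler model.** Exponential times, treatment HR 1.5, score 4 reaching its target at 0.5, 2 or 3 times the rate of score 3 (1,500 trials per setting). The average HR is 1.40 to 1.48 without score and 1.50 to 1.51 stratified. With equal rates there is no attenuation.

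**The case against.** - **Direction and pooling.** The either-direction probability must not be paired with a one-direction consequence, and pooled ranges hide where the extremes lie. This stands as a matter of reading. A re-run placed the top of the range (56.2% / 14.5%) at a 90% score-4 share with every score-3 patient staying at 2 for a median of 14 days. There, a 9-patient gap in that direction has probability 1.6%. At 50 or 70% the same lag gives about 49–51% / 8–9%. Typical gaps are smaller, averaging 5.3, 4.8 and 3.1 patients. A gap of 5 at 70%, with half staying 7 days, gives 26.5% / 4.3%.
- **Undocumented mechanism.** No passage gives the lag at score 2, and the score is recorded at discharge, so a score-3 entrant may already be scored 1 there. If none stay at 2, the planned model is at or below nominal for this direction of imbalance, apart from small excesses when failure is unrelated to score. Entry also requires "Oxygen saturation <94% in room air at screening", which may make score 3 uncommon. This limits the size, not the defect.
- **Existing safeguards.** The ordinal model adjusts for score, time to score 2 or lower has one target for everyone, and SAP 7.4 tabulates baseline score by arm. A reader could see an imbalance, but the planned hazard ratio would still not correct for it.
- **Simulation gaps.** The model's two covariates and the first censoring rule were not simulated. If authorised-treatment use tracks oxygen need, stratified randomisation and adjustment would reduce the effect. That stands.

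**Conclusion.** The concern holds, as an improvement to consider for one secondary analysis. The two entry scores have different targets, and the Cox model omits the variable that sets them. There is no departure from the protocol and no average inflation of type I error. The primary analysis is untouched, and the score ≤2 and score 0 endpoints are not affected because each has one target for all.

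The harm is conditional on a chance imbalance. With 9 extra score-4 patients on antroquinonol, the planned model's null positive rate at one-sided 0.2 ranges from 9.5% to 56.2%. The score-stratified model stays at 18.6–22.2%. Stratifying removed the shift in every setting run; whether it gains power depends on assumptions. All sizes rest on an assumed 3/4 split, discharge pattern, time spent at score 2, and link between score and failure. Confidence in the size is therefore medium.

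**What to change.** Before unblinding, stratify the Cox model for time to 2-point improvement, and only that model, by baseline WHO score (3 vs 4). Keep treatment, authorised-treatment use and age as covariates. Stratifying is preferable to a numeric covariate because two groups with different events need not have proportional hazards. SAP 6.1 already defines the value: "Baseline value is defined as the last scheduled or unscheduled value collected prior to the first dose of study treatment". Add a rule for any baseline score other than 3 or 4, and state whether a 2 imputed under SAP 6.2 counts as an event. Specify Efron ties, since events fall on few days. Keep the two-covariate model as a sensitivity analysis and record the change in SAP section 8, which now declares none. Leave the score ≤2, score 0 and primary models unchanged.

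The cost is a few sentences and no new data, since the score is collected at screening and Day 1. The hazard ratio becomes conditional on the score. Power can fall: by up to 3.2 points at one-sided 0.2 and 5.2 at 0.025 in the settings tabulated, mainly when failures concentrate in score-4 patients; by up to 1.7 / 2.0 points when score-3 patients are already at 1 or lower at discharge.

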4.4.2. Hepatic injury or renal impairment

4.4.2.1. *Hepatic injury*

Discontinuation of study treatment for abnormal liver tests should be considered by the investigator when a patient meets one of the conditions outlined in [Figure 2](#) or if the investigator believes that it is in the best interest of the patient.

Figure 2: Stopping Criteria for Liver Injury

Abbreviations: ALT = alanine aminotransferase; INR = international normalized ratio; ULN = upper limit of normal
 Note: INR value is not applicable to patients on anticoagulants.

4.4.2.2. *Renal impairment*

If a patient has renal impairment (creatinine clearance <50 mL/min), treatment should be discontinued.

4.4.3. **Discontinuation of study treatment**

A patient may be discontinued early from study drug treatment (ET of study treatment) for the following reasons:

- Lack of efficacy (e.g. patients who require nonstudy antiviral or anticytokine therapy due to progression of COVID-19), and the investigator's decision. Note: remdesivir or other authorized treatments for COVID-19 is allowed if considered SoC, if started prior to randomization or during the study. Initiation of remdesivir or other authorized treatments for COVID-19 during the study will be considered a treatment failure if started due to progression of disease.
- Adverse event
- Withdrawal by patient (specify reason in the eCRF)
- Lost to follow-up
- Death

- Physician decision (i.e. investigator decision based on protocol deviation, assessment that it is not in the patient's best interest to continue, or other reason [specify reason in the eCRF]).
- Sponsor decision (specify reason in the electronic case report form [eCRF])

No temporary treatment discontinuation is permitted.

Patients who discontinue study treatment prematurely will be asked about the reason(s) for discontinuation and will be asked to continue all assessments up to Day 28. Patients will be educated about the continued scientific importance of their data and encouraged to complete the Day 28 Follow-up/EOS assessments even if they discontinue study treatment prematurely.

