6.2. Prohibited medications

Simultaneous participation in other clinical treatment study protocols is not allowed.

Treatment with any antiviral drugs (except remdesivir or other authorized treatments for COVID-19), or with any drugs known to be strong inhibitors or inducers of CYP2C19, 3A4, 2C8, and 2E1 are prohibited within 14 days or 5 half-lives prior to the start of study treatment. Drugs with a narrow therapeutic index that are substrates of 1A2, 2B6, 2C8, 2C9, 2C19, 3A, and 2D6 are also prohibited.

A list of commonly known CYP inducers and inhibitors is given in [Appendix 6](#) for reference use.

Antroquinonol is a purified compound from an extract of *A. camphorata*. For this reason, the use of *A. camphorata*-containing products is prohibited within 2 weeks prior to the first administration of study drug, and the use of *A. camphorata*-containing products other than antroquinonol is prohibited throughout the study.

Patients who begin to receive nonstudy antiviral medication after the start of study treatment will be discontinued from study treatment. Note: remdesivir or other authorized treatments for COVID-19 is allowed if considered SoC, if started prior to randomization or during the study. Initiation of remdesivir or other authorized treatments for COVID-19 during the study will be considered a treatment failure if started due to progression of disease.

Administration of an authorized COVID-19 vaccines is permitted as per the local health authority recommendation.

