8.4.2. Secondary efficacy outcome measures

Clinical improvement measured as a score on the WHO COVID-19 Clinical Improvement Ordinal Scale will be analyzed at each timepoint, adjusted for the clinical improvement score at baseline, age at baseline, and remdesivir or other authorized treatments for COVID-19 use at baseline, using an ordinal logistic regression on Days 7, 14, and 28. In addition, descriptive statistics will be provided for average score, and the proportion of patients at or below each score, at each timepoint. Time to 2-point improvement from baseline in WHO COVID-19 Clinical Improvement score, time to score of 2 or lower, and time to score of 0, will also be analyzed.

The hazard ratio and its 95% confidence interval for time to event outcomes will be estimated by Cox proportional hazard model, with patients censored at the time they are provided any antiviral therapy not prescribed at baseline, or on Day 28 if they have not yet recovered. Patients who die at any time will be considered not yet recovered by Day 28. Median time to 2-point improvement, time to score of 2 or lower, and time to score of 0 will be estimated by Kaplan-Meier (KM) method, and the KM curve will be provided. The p-value for comparison between groups will be obtained based on proportional hazards modeling stratified by the same covariates as the primary model.

Duration of hospitalization and ICU stay up to Day 28 will be analyzed using normal regression, using the same covariates as for the primary endpoint. Patients who die will be considered as continuing to require hospitalization or ICU stay up to Day 28 for the purposes of this analysis.

Time to virological clearance, measured as study days from start of treatment to first negative SARS-CoV-2 PCR test, will be evaluated using similar statistical methods as clinical

improvement. All patients who have died will be considered as not having cleared the virus by Day 28

Rate of change in viral load will be summarized descriptively and estimated using a Mixed Model for Repeated Measurements model. The model will include the treatment group, age, remdesivir or other authorized treatments for COVID-19 use at baseline, visit, and the interaction between visit and the treatment group as fixed factors, and will include the baseline value as a covariate. If a patient has tested negative, they are assumed to be negative until they are tested again.

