### 7.6.2.3 SARS-CoV-2 PCR Test

Time to virological clearance, measured as study days from start of treatment to first negative SARS-CoV-2 PCR test, will be evaluated using similar statistical methods as clinical improvement where in this case, the first negative SARS-CoV-2 PCR test is considered as an event. Patients will be censored on Day 28 if they have not yet shown SARS-CoV-2 PCR negative or have died by Day 28.

If quantitative SARS-CoV-2 PCR results are available, the following analyses will be conducted. Note that if a patient has tested negative, they are assumed to be negative until they are tested again and for negative test result, viral load is assumed to be half of the lower limit of detection.

- Rate of change in viral load will be estimated using a Mixed Model for Repeated Measurements model.

The model will include the treatment group, age at baseline ( $> 65$  years vs  $\leq 65$  years), remdesivir or other authorized treatments for COVID-19 use at baseline (yes vs no), log (viral load) at baseline, study day (numerical, 0 for baseline), and the interaction between study day and the treatment group as fixed factors, patient as random factor (random intercept and random slope).

The model will use natural-log-transformed viral load as the response variable.

An unstructured covariance structure will be used. In case of a convergence problem with the unstructured covariance matrix, the following structures with robust sandwich estimator for the standard error of the fixed effect estimates will be assessed in a sequential fashion: heterogeneous Toeplitz, heterogeneous first-order autoregressive, Toeplitz and compound symmetry.

The estimate of the study day\*treatment will be interpreted as the difference between treatment and placebo groups in terms of the rate of change in viral load. The estimate, standard error and p-value of study day\*treatment will be reported.

- Natural-log-transformed viral load with change from baseline will be summarized by treatment group and visit using descriptive statistics.
- Arithmetic mean (+SD) of natural-log-transformed viral load vs. time figure for each treatment group will be presented.

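### Two unranked censoring rules for the clinical-improvement time-to-event endpoints, one of them informative when new therapy follows progression, and neither declared as a change from the protocol (minor)

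*SAP*

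**What the plan says.** **Protocol 8.4.2** has one rule for these time-to-event outcomes: a Cox model "with patients censored at the time they are provided any antiviral therapy not prescribed at baseline", otherwise at Day 28. Patients who die count as not recovered by Day 28.

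**SAP 7.6.2.1** states that "The analysis will be carried out using two different censoring rules". Rule 1: "Patients will be censored at the time they are provided any authorized treatment for COVID-19 not prescribed at baseline", otherwise at Day 28. Rule 2: "Patients will only be censored on Day 28 if they have not yet recovered or have died by Day 28". One p-value and one set of medians are then promised, with no statement of which rule they come from. SAP 3.2 marks time to score 2 or lower and time to score 0 as supportive; that ranks endpoints, not censoring rules.

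**SAP 7.6.2.3**, on virological clearance, refers to methods similar to those for clinical improvement but gives only Day-28 censoring: "Patients will be censored on Day 28 if they have not yet shown SARS-CoV-2 PCR negative or have died by Day 28".

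**Protocol 4.4.3 and 6.2** say that authorised COVID-19 therapy begun during the study "will be considered a treatment failure if started due to progression of disease".

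**SAP 7.1** applies two one-sided marks to results: 0.025 for significance and 0.2 for a promising trend. **SAP section 8** reports that the statistical methods are unchanged from the protocol.

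**The concern.** There are three linked problems.

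- **No lead.** If the two rules disagree, nothing in the SAP says which result is the finding, so the more favourable one can be put forward.
- **Informative censoring under rule 1.** Censoring treats the patient as having the same prospects as those still at risk. A patient given new therapy because the disease has progressed does not. A patient who starts therapy and later dies can also leave the risk set at the start of therapy, although Protocol 8.4.2 counts deaths as not recovered by Day 28; neither document says which provision takes precedence. Starts of authorised standard of care for reasons other than progression need not be informative.
- **Undeclared change.** Rule 1's trigger is not the protocol's, rule 2 is not in the protocol, and section 8 lists neither.

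At stake are the hazard ratios, p-values and medians of the clinical-improvement endpoints, and the traceability of the SAP to the protocol.

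**Working it through.** **Plan's own figure.** The documents give no event count, hazard ratio or power for these endpoints. The stated 80% power with 174 patients (78% vs 89%, one-sided 0.2) belongs to the Day-14 endpoint. Simulated with both futility looks and 85 evaluable per arm (174 x 0.98 = 170.5), it comes to 79.9%. It reproduces and has no bearing here.

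**Step 1: the rules side by side.**

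| | Protocol 8.4.2 | SAP rule 1 | SAP rule 2 |
|---|---|---|---|
| Censoring before Day 28 | new antiviral | new authorised COVID-19 treatment | none |
| Otherwise | Day 28 | Day 28 | Day 28 |
| Status | only analysis | not ranked | not ranked |

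**Step 2: mechanism.** Assume a recovery hazard of 0.10/day, falling to 0.025 or 0.05/day after progression, and a drug whose only effect is to halve progression from 22% to 11% (borrowed from the Day-14 failure assumptions). If all progressors start new therapy at once and patients are otherwise alike, everyone left at risk under rule 1 has hazard 0.10 in both arms, so HR = 0.10/0.10 = 1.00. The real benefit is deleted. Rule 2 keeps the slow recovery of progressors in the comparison.

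**Step 3: size** (HR above 1 favours antroquinonol).

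*Simulation A:* 300,000 patients per arm, no deaths, hazards as in step 2, with or without gamma frailty (variance 0.5) under which slow recoverers progress more often; progression over Days 1-7 or 1-14; all or half of progressors start therapy, at once or within 0-3 days; 32 settings.

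*Simulation B:* median recovery 8 days in non-progressors; progression on Days 1-10; hazard afterwards 0.1-0.5 of usual; 25-100% of progressors start therapy; progression 22% on placebo and 11%, 22% or 33% on drug (the Protocol 8.1 scenarios).

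| Case | Rule 1 HR | Rule 2 HR |
|---|---|---|
| A, drug halves progression | 0.97-1.06 | 1.03-1.10 |
| A, drug doubles progression | 0.94-1.04 | 0.91-0.98 |
| B, effective (11%) | 1.06-1.20 | 1.12-1.23 |
| B, harmful (33%) | 0.83-0.93 | 0.81-0.89 |
| A and B, identical arms | about 1.0 | about 1.0 |

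In B the placebo Kaplan-Meier recovery by Day 28 is 0.78-0.90 under rule 1 and 0.75-0.85 under rule 2. The widest placebo gap with an effective drug is 0.895 - 0.750 = 0.145.

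Gap on the log-HR scale: the largest single setting in B is ln(1.218/1.064) = 0.135. In A the ends of the ranges bound it at ln(1.10/0.97) = 0.126 and ln(1.04/0.91) = 0.134. The standard error at 87 per arm is 0.16-0.18; by SE = sqrt(4/d) that corresponds to d = 4/0.16² = 156 down to 4/0.18² = 123 recoveries among 174. Every gap is below one SE.

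**Step 4: cost of the open choice**, with no drug effect and equal progression and starts. P(either) = P(rule 1) + P(rule 2) - P(both). For one case in A (6,000 trials of 87 per arm): 0.197 + 0.198 - 0.130 = 0.265, and the rules disagree in 0.265 - 0.130 = 0.135 of trials.

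| Mark | One rule alone | At least one: A | At least one: B |
|---|---|---|---|
| 0.2 | 0.19-0.21 | 0.235-0.270 | 0.235-0.276 |
| 0.025 | 0.024-0.027 (B) | not run | 0.031-0.040 |

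**The case against.** The strongest reply is that both rules are prespecified and both will be run, the endpoints are secondary, and the gap is within one standard error. A rise from 20% to 23-28% is also small beside many secondary endpoints analysed in three populations without a multiplicity plan. All of that stands and is why the point is minor. It does not settle which result is quoted when the rules disagree, and it does not make the section 8 statement accurate. Rule 1 is listed first and lies closest to the protocol, so it might be taken as the default, but the SAP does not say so. Leading with rule 2 is a choice of estimand that moves further from the protocol, which is a reason to declare it.

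Four stronger readings are tempting and not supported:

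- *Rule 1 reverses the direction of effect.* In simulation A it falls below 1 for a helpful drug only with frailty and nearly all progressors treated. In B it never crosses 1.
- *Unequal use of new therapy between arms creates a false signal under rule 1.* The trial is double-blind, and the documents give no basis for starts that differ between arms with the same disease course.
- *The new trigger brings in non-antiviral drugs.* Protocol 4.4.3 mentions "patients who require nonstudy antiviral or anticytokine therapy due to progression of COVID-19" as an example of lack of efficacy, a reason for stopping study drug, and then separately permits authorised treatments. It does not show that the authorised group contains non-antivirals. Protocol 6.2 words authorised treatments as an exception within antivirals, so the SAP may only be harmonising terms. The wording still differs and should be declared.
- *The treatment-failure label contradicts the analysis.* It sits among the reasons for stopping study treatment and reads most naturally as a disposition label, so no protocol edit is needed.

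**Conclusion.** The point holds, at minor severity. On the text alone, two censoring rules are unranked, rule 1's trigger differs from the protocol's, rule 2 is an addition, and section 8 is inaccurate in reporting no change. On the statistics, rule 1 is informative wherever new therapy follows progression. It generally pulls the hazard ratio towards 1 whether the drug helps or harms, and it overstates Kaplan-Meier recovery in both arms. This weakness is inherited from the protocol's own rule; rule 2 is the improvement and only lacks its rank.

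All sizes rest on assumed recovery hazards, progression rates and shares of progressors treated, because the documents give no rate of new therapy starts. With identical arms neither rule biases the hazard ratio; only the free choice between them costs anything. A reader might infer that the trial's main conclusion is at risk. It is not: the Day-14 primary endpoint does not use either censoring rule.

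**What to change.** Before unblinding:

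- **SAP 7.6.2.1.** Name rule 2 as the main analysis for all three time-to-event endpoints, supplying the hazard ratio, p-value and median, and rule 1 as supportive, with a note that its censoring is informative when therapy follows progression. Rule 2 is workable because patients who stop study drug early "will be asked to continue all assessments up to Day 28".
- **Repair rule 2 in the same place.** Read literally, it keeps living patients who withdraw or are lost (Protocol 4.4.4 and 4.4.5) at risk to Day 28 as if observed. Censor them at their last assessment and keep deaths as not recovered to Day 28. At the assumed 2% drop-out this concerns about 174 x 0.02 = 3.5 patients.
- **SAP section 8.** List the changed trigger in rule 1, the added rule 2, the choice of lead, and the Day-28-only censoring for virological clearance.

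The cost is a few lines in the SAP, with no added patients, visits or data, since both analyses are already planned. The downside is that the main estimate then includes the effect of later authorised therapy; rule 1 stays in the report for readers who want the other view. The change concerns only how events are counted, not when therapy is given.
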